5.3 SCHEMA

6.0 STUDY TREATMENT

Given the extensive range of possible instrumentation for this procedure, the choice of instrumentation

for the laparoscopic or robotic approach will be left to the discretion of the surgeon.

At the commencement of surgery, a thorough inspection of all peritoneal surfaces should be performed

including direct inspection of the diaphragm. The location of any metastatic disease should be

documented in the operative report and a biopsy should be performed to confirm the diagnosis. If

intraperitoneal cancer is detected, the aim of treatment should shift to palliation and the radical

hysterectomy should be abandoned.

The pelvic lymphadenectomy may be performed before or after the radical hysterectomy and the

sequence choice will be left to the discretion of the physician. Decision planning regarding continuing

the radical hysterectomy based on intraoperative status of lymph nodes will be left to the discretion of

the physician. In patients undergoing sentinel node identification and lymphatic mapping, the choice of

that technique is left to the discretion of the individual surgeon.

Patients who undergo sentinel node identification will undergo a complete pelvic lymphadenectomy.

This includes common iliac lymph nodes. The time allocated to sentinel node identification should be

noted separately in the operative report.

In patients with macroscopic evidence of metastatic disease to the pelvic lymph nodes based on

intraoperative assessment, a complete pelvic lymphadenectomy is not required and the radical

hysterectomy may even be abandoned. Such patients should have a para-aortic lymph node sampling

to determine extent of disease, with this being at the discretion of the individual surgeon.

During the operative procedure, the surgeon should document the specific surgical instruments used in

patients randomized to the laparoscopic/robotic approach. The surgeon should also note in the

operative report the following information:

• Operative time from start of radical hysterectomy, as documented by skin incision, until all

trocar sites have been closed or abdominal incision is closed.

Version 4 October 2014 LACC Trial Page 26 of 105

- Blood loss
- Intraoperative complications
- Reasons for conversions to laparotomy in patients randomized to the laparoscopic or robotic approach
- For patients who undergo a robotic radical hysterectomy, the time that was taken to set up and dock the robot should be noted in the operative note and subtracted from the total procedure time.
- For patients who undergo a para-aortic lymph node dissection, the time taken to do this
 procedure should be noted in the operative note.

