|---------------------------|---------------------------------------------------------------------------------------------------------------------------------------------------------------------------------------------------------------------------------------------------------------------------------------------------------------------------------------------------------------------------------------------------------------------------------------------------------------------------------------|--|
| Experimental Treatment | Total Laparoscopic (TLRH) or Robotic Radical Hysterectomy + laparoscopic pelvic and +/- para aortic lymph node dissection Disease-Free Survival (DFS) | |
| Primary Outcome | | |
| Secondary Outcomes | Recurrence: Pattern/Site of recurrence Morbidity: Intraoperative, perioperative, early postoperative (<4 weeks) and long-term morbidity (4 weeks to 6 months); transfusion requirements; postoperative pain and analgesic consumption Treatment costs Quality of Life Pelvic Floor function Overall Survival at 4.5 years follow-up. Feasibility of sentinel lymph node biopsy in this group of patients | |

GLOSSARY OF ABBREVIATIONS

AAGL American Association of Gynecologic Laparoscopists

ABS American Brachytherapy Society

AE Adverse event

AJCC The American Joint Committee on Cancer

CDMU Central Data Management Unit

CONSORT Consolidated Standards of Reporting Trials

CORE The Centre on Outcomes, Research and Education

CT Computed tomography

CTCAE V3.0 Common terminology criteria for adverse events Version 3.0

CRF Case Report Form

DFS Disease free survival

DSMC Data safety monitoring committee

EBRT External beam radiotherapy

ECG Electrocardiogram

ECOG Eastern Cooperative Oncology Group

eCRF Electronic case report form(s)

EQ-5D EuroQoL-5d

FACT-CX Functional assessment of cancer therapy – cervix

FIGO Federation of Gynecologists and Obstetricians

FDA Food and Drug Administration

GCP Good clinical practices

GOG the Gynecologic Oncology Group

GP General Practitioner

HADS Hospital Anxiety and Depression Scale

HREC Human Research Ethics Committee

IB Investigational brochure

ICH International Conference on Harmonisation

IC-Green Indocyanine Green for Injection

IDMS Isotope-dilution mass spectrometry

IRB Institutional Review Board

IOLM Intra-operative Lymphatic Mapping

ITT Intent to treat

LACC Laparoscopic Approach to Cervical Carcinoma

LARVH Laparoscopy-assisted radical vaginal hysterectomy

LDR Low Dose Rate

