11.0 ANALYSIS OF COST EFFECTIVENESS

Participation in the economic analysis component is optional for study sites and analyses will be country specific.

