11.1 ECONOMIC ANALYSIS

We will assess the cost-effectiveness of the intervention (TLRH \pm Laparoscopic Pelvic/Aortic Lymph Node Dissection) relative to standard treatment alone (TARH \pm Pelvic/Aortic Lymph Node Dissection), calculated as the incremental cost per unit of improvement in functional outcome, and measured in terms of the primary outcome.

The outcomes of this part of the economic analysis will be in terms of costs per disease and treatment specific difference in quality of life at six months. More specifically, costs per fewer days' treatment-related morbidity, shorter hospital stays, less days with post-operative pain, and less analgesic consumption. By assessing the difference in cost between the standard treatment and the proposed intervention, it can be ascertained which of the two treatments represents the most sound investment in terms of the improvement in quality of life.

We will also measure the quality-adjusted life years (QALYs) gained with the intervention and use this to undertake a cost-utility analysis. The QALY calculations will be based on health status measures for trial participants, with valuations of changes in health status and quality of life based on the EQ-5D. Several viewpoints will be considered for the economic analyses, including those of health system purchasers, households and society in general.

This part of the economic analysis allows us to express outcomes in costs per QALY. The aim of this generic outcome measure is to assess whether the study intervention represents value for money as compared to alternative interventions (including for other conditions), and as compared to the various threshold values below which an intervention is considered good value for money (in Australia \$40,000 per QALY is often used).

In terms of measuring costs, a number of components will be considered, including: the intervention costs; the provision of information booklets to patients; GP and specialist consultations; radiology and imaging; prescriptions, over-the-counter medications; community health and social services; days off work; and informal care by family and friends. Direct costs will be obtained for samples of patients, stratified by hospital, operation and outcome, using a bottom-up approach by recording the volume of resource use in both arms of the trial, and then applying a unit cost to each component. Data on all patients' use of healthcare services will be collected using a combination of retrospective

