* OR time for sentinel node biopsy should be noted as a separate procedure in operation report (Specific recording requirements for the sentinel node biopsy and intraoperative lymphatic mapping are located in Section 6.0).

** TLRH.TRRH/TARH: OR time should include the start of the procedure until all trocar sites/abdominal incisions are closed.

^{***} For patients randomized to laparoscopy (not robotic), the surgeon should document specific surgical instruments used for the procedure

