| Date of Histopathology Report yyyy/mm/dd Histological Grade:- Well-differentiated (G1) Moderately differentiated (G2) Poorly differentiated (G3) Tumour Size | mm De | mm pth | | | | |
| Date of Histopathology Report yyyy/mm/dd Histological Grade:- Well-differentiated (G1) Moderately differentiated (G2) Poorly differentiated (G3) Tumour Size Depth of Cervical Invasion Please give a brief description of any invasion e.g. lymphovascular, perineural, | mm De | mm pth | | | | |

LACC Histopathology Translation Form Version 1

17 March 2014

- LABEL EACH SOURCE DOCUMENT WITH PATIENT NUMBER
- PLEASE DE-IDENTIFY PATIENT DETAILS
- PLEASE LABEL ALL SOURCE IN ENGLISH

| | pic Approach to Cervical Carcino LACC | ma | |
|--------------------------------------------------------------------------------------------------------------------------|------------------------------------------|-------|------|
| Patient Initials and Number: | | | |
| | | | |
| Surgary ' | Franslation Form | | |
| 1 | int and use a black pen | | |
| a rease ja | an and use a mark pea | | |
| Surgical Details | | | |
| Date of Surgery | | | |
| Date of Admission for Surgery | yyy/mm/dd | | |
| 20 8 24 5 20 10 10 10 10 10 10 10 10 10 10 10 10 10 | yyy/mm/dd | | |
| Date of Discharge | vyy/mm/dd | | |
| Total Laparoscopic/Robotic Ra | adical Hysterectomy | | |
| Robotic/Laparoscopy co | nverted to Laparotomy Yes No | | |
| Robotic/Laparoscopy cor Robotic converted to Lap | nverted to Laparotomy Yes No | | |
| Robotic/Laparoscopy cor Robotic converted to Lap Specify reasons: If either surgery abandoned Specify reasons: | nverted to Laparotomy Yes No | | |
| Robotic/Laparoscopy con Robotic converted to Lap Specify reasons: | nverted to Laparotomy Yes No | Yes □ | No 🗆 |

1

| Patient Initials and Number: | | |
|--------------------------------------------------------------------------------------------------------------|-----------------------|---------------------|
| | | |
| Surgery Translation Form | | |
| Ouration of operation | Start Time hh: nun | Finish Tim hh:mm |
| Estimated Blood loss (ml) | Anno dele | |
| SOURCE ATTACHED | Yes 🗆 | No 🗆 |
| Did the Patient have a blood transfusion during surgery or post operatively up until date of discharge date? | Yes 🗆 | No 🗆 |
| | 2 | Manufacture Co. |
| Date of Post Op Day 1 Haemoglobin (if performed) yyyy/mm/dd SOURCE ATTACHED | Yes 🗆 | No 🗆 |
| Please add a brief description of the surgical event e.g. type of surgery, observations. | | |

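### Section 6.0 subtracts robot set-up and docking time from procedure time, which conflicts with its own incision-to-closure definition and with Appendix 1, so robotic cases have two incompatible operating times

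*Protocol*

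**What the plan says.** Three places in the protocol fix how long an operation lasted.

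- **Section 6.0, general item.** The operative report is to give "Operative time from start of radical hysterectomy, as documented by skin incision, until all" trocar sites, or the abdominal incision, are closed. This applies to both arms and mentions no deduction.
- **Section 6.0, robotic item.** The time taken to set up and "dock the robot should be noted in the operative note and subtracted from the total procedure time". This applies to robotic cases only.
- **Appendix 1, notes to the schedule.** Under a label naming all three procedures, "OR time should include the start of the procedure until all trocar sites/abdominal incisions are closed". No deduction is mentioned.

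Two further places bear on how the figure is captured and used. The surgery translation form in Appendix 10, for non-English-speaking sites, asks for the start and finish times of the operation and has no entry for docking or net time. Section 11.1 describes a "bottom-up approach by recording the volume of resource use in both arms of the trial" and names the cost components in general terms: "In terms of measuring costs, a number of components will be considered, including: the intervention costs", followed by others.

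**The concern.** A surgeon or data manager with a robotic case cannot satisfy all three instructions. Following the robotic item gives a net time; following the general item or Appendix 1 gives a gross time. The deduction can arise only in the experimental arm, and there only in its robotic part. No step of open or conventional laparoscopic surgery is taken off the clock in a matching way.

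At stake is the comparability of operating time between approaches and between sites. If net times are compared with gross times, the robotic approach looks quicker than it was on the protocol's own incision-to-closure definition. A costing that took theatre minutes from this field would carry the same tilt. Because this is an instruction to the surgeon at the point of recording, a later analysis plan could not be sure of sorting net from gross times.

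**Working it through.** The protocol states no figure for this point, so there is none to reproduce. The check compares the definitions and then gives a sense of scale.

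**1. The definitions side by side.** For one robotic case, let T be the time from skin incision to closure, A the set-up done before incision, and B the set-up and docking done after incision.

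| Source | Recorded duration |
|---|---|
| Section 6.0, general item | T |
| Section 6.0, robotic item applied to T | T − (A + B) |
| Appendix 1, if the procedure starts at incision | T |
| Appendix 1, if it is taken to start before incision | more than T |
| Appendix 10 surgery form | finish − start, gross |

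The robotic item differs from the others whenever A + B is above zero. It is also wrong on its own logic: only B lies on a clock that starts at incision, so a consistent net time would be T − B. The written rule takes off a further A that was never counted. The protocol does not say how set-up and docking divide between A and B.

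**2. Treatment of other separable steps.** Section 6.0 asks for sentinel-node time and para-aortic dissection time to be noted. It does not order either to be subtracted. Section 6.1, on the open procedure, removes nothing from the clock. Robot set-up and docking is the only deduction.

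**3. Who is affected.** The experimental treatment in the synopsis is "Total Laparoscopic (TLRH) or Robotic Radical Hysterectomy + laparoscopic pelvic and +/- para aortic lymph node dissection". The deduction is zero for conventional laparoscopy and A + B for robotic cases. Hence:

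shift in experimental-arm mean = robotic share × (A + B)

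**4. Scale, on assumed inputs.** Neither term on the right is in the protocol. Assume a robotic share of 10% to 50% and A + B of 10 to 30 minutes. For the denominator, use the 205-minute average that Section 2.4 cites from a laparoscopic series, the only kind of operating time the protocol offers.

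- Lower end: 0.10 × 10 = 1 minute; 1/205 = 0.5%.
- Upper end: 0.50 × 30 = 15 minutes; 15/205 = 7.3%.
- Per robotic case: 10/205 = 4.9% to 30/205 = 14.6%.

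These figures show only how the effect scales. They do not estimate what happened in this trial.

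**The case against.** The strongest reply is that little depends on this field. Operating time is not among the objectives in Section 1.0 or the outcomes in Sections 7.1 and 7.2, and Section 10.2 names no analysis of it. Disease-free survival is unaffected. The subtracted minutes must themselves be noted, so gross time can be rebuilt from the operative note. Net time is also a legitimate quantity to report if it is labelled as such.

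Much of this stands, and it is why the point is minor. It does not remove the contradiction. Rebuilding gross time requires knowing which cases were entered net, and no instruction asks sites to say so. The translation form has no docking field. The electronic case report form is not shown, so it may or may not have one.

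A reader might also infer more than the text supports:

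- **That operating time is understated for the experimental arm as a whole.** It is understated only for robotic cases, and the arm also contains conventional laparoscopic ones in unknown proportion.
- **That the protocol builds a theatre cost on the reduced time.** Section 11.1 names neither theatre nor operating time, and does not say that net time is the resource unit. Section 11.0 adds: "Participation in the economic analysis component is optional for study sites". A cost bias is conditional on a costing that uses this field.
- **That a definite percentage bias can be stated.** Any percentage rests on assumed docking minutes divided by laparoscopic, not robotic, operating times.

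**Conclusion.** The contradiction is certain from the text. The Section 6.0 robotic item cannot be reconciled with that section's incision-to-closure definition or with the Appendix 1 rule. Its direction is also clear: if followed, recorded time is too short for robotic cases and for no others, possibly by more than the time spent on the robot after incision.

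The size is not determinable from the protocol. The range of 1 to 15 minutes on the arm mean rests wholly on the assumed robotic share and docking time. An effect on cost arises only if a site takes part in the economic component and costs theatre time from this field. Severity: minor. It is worth correcting because the conflict sits in the recording instruction and the remedy is nearly free.

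**What to change.** - In Section 6.0, delete the clause that orders the subtraction and keep the requirement to note set-up and docking time.
- Use one gross definition, skin incision to closure, in both arms. Align Appendix 1 with it: its reference to the start of the procedure does not say skin incision and can be read as an earlier point.
- Record set-up and docking time as a separate item, split into before and after incision, and add it to the Appendix 10 surgery form.
- State that wherever costing uses theatre time, it takes the gross time plus any separately recorded set-up before incision. Incision-to-closure time alone would miss that set-up.
- For robotic cases already entered, check against the operative note whether the recorded duration is gross or net.

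The cost is a change of wording, one added form item and a check of existing robotic records. Recorded robotic time becomes slightly less favourable. Net time can still be described, under its own label.

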6.1 STANDARD TREATMENT: TARH + PELVIC/AORTIC LYMPH NODE DISSECTION

- Preoperative antibiotic is given at least 15 minutes before skin incision;
- Apply sequential compression device (SCD)
- Positioning in the supine or lithotomy position;
- Given the extensive range of possible instrumentation for this procedure, the choice of instrumentation for the laparoscopic approach will be left to the discretion of the surgeon.
- Vertical midline or lower transverse incision;
- A thorough inspection of all peritoneal surfaces should be performed including direct inspection of the diaphragm. The location of any metastatic disease should be documented in the operative report and a biopsy should be performed to confirm the diagnosis.
- The lateral pelvic spaces are opened and bulky, suspicious lymph nodes are removed if feasible and submitted for frozen section examination. If those lymph nodes are positive, aortic lymph nodes are sampled but the radical hysterectomy procedure will be abandoned and the patient is referred to definitive chemoradiotherapy.
- If the pelvic nodes are not suspicious, a radical hysterectomy (Piver type 2 or 3) with or without bilateral salpingo-oophorectomy is performed;
- Ovaries may be removed or preserved and/or transposed.
- A pelvic lymph node dissection includes removal of the lymph nodes along the external iliac artery, the internal iliac artery and the common iliac artery as well as in the obturator fossa;
- An aortic lymph node dissection for staging purposes would include removal of the lymphoid tissue up to the level of the inferior mesenteric artery;

- Intra-abdominal drains are not mandatory;
- Mass closure of sheath, skin closure.
- Indwelling catheter (days documented) according to local protocol.

6.2 INTERVENTION: TLRH or TRRH + LAPAROSCOPIC PELVIC / AORTIC LYMPH NODE DISSECTION

- Preoperative antibiotic is given at least 15 minutes before skin incision;
- Apply sequential compression device (SCD)
- Positioning in the lower lithotomy position with the arms parallel to the patient or the arms resting on the patient's chest;
- Given the extensive range of possible instrumentation for this procedure, the choice of instrumentation for the laparoscopic approach will be left to the discretion of the surgeon.
- The laparoscopic entry technique and the number of ports used to perform the procedure are up to the surgeon's discretion.
- A thorough inspection of all peritoneal surfaces should be performed including direct inspection of the diaphragm. The location of any metastatic disease should be documented in the operative report and a biopsy should be performed to confirm the diagnosis.
- Transection of the round ligament in order to enter the retroperitoneum. The lateral pelvic spaces are opened and bulky, suspicious lymph nodes are removed if feasible and submitted for frozen section examination. If those lymph nodes are positive, aortic lymph nodes are sampled but the radical hysterectomy procedure will be abandoned and the patient is referred to definitive chemoradiotherapy.
- If the pelvic nodes are not suspicious, a radical hysterectomy (Piver type 2 or 3) with or without bilateral salpingo-oophorectomy is performed;
- Ovaries may be removed or preserved and/or transposed.
- A pelvic lymph node dissection includes removal of the lymph nodes along the external iliac artery, the internal iliac artery and the common iliac artery as well as in the obturator fossa;
- A tube or a similar device for uterine mobilization is inserted transvaginally, the bladder peritoneum is reflected and the bladder pillars are lateralized over the edge of the tube;
- The uterine artery is identified, secured and divided at the level of the origin of the internal iliac artery;

- The parametria and the uterosacral ligaments are dissected. A sufficient surgical margin is aimed for. The vagina is circumcised over the vaginal tube and the specimen is removed through the vaginal tube;
- A systematic pelvic lymph node dissection is performed, which includes removal of external iliac nodes, obturator nodes, and common iliac nodes ± removal of the aortic nodes up to the level of the inferior mesenteric artery;
- The tube is used as a conduit to remove the lymph nodes from the abdominal cavity or the lymph nodes may be removed through an endo-catch bag;
- Closure technique for the vaginal vault is left to the discretion of the surgeon;

6.3 INTERVENTION: INTRAOPERATIVE SENTINEL LYMPH NODE (SLN) IDENFICATION WITH ISOSULFAN BLUE AND HAND HELD GAMMA COUNTER OR WITH INDOCYANINE GREEN (IC-Green™.

Injection of radionuclide

- a. Inject 0.5 mCi to 1.0 mCi of radiolabeled Tc-99 sulfur microcolloid (volume 1.0-4.0 ml) in four divided doses around the tumor or into the 12, 3, 6, and 9 o'clock positions if the tumor involves the endocervix. The volume for injection is small; therefore, take care to preserve enough radionuclide to inject in all 4 quadrants.
- b. The radionuclide may be injected in the nuclear medicine suite up to 6 hours prior to the sentinel lymph node procedure or in the operating room after induction of anesthesia prior to prepping and draping of the patient. The radionuclide should not be injected at the same time as the blue dye since the blue dye will reach the sentinel node more quickly than the radionuclide.
- c. Other radionuclide's may be substituted if Tc 99 labeled sulfur microcolloid is not available.

Injection of Blue Dye

- a. The patient must be positioned, prepped and draped so that a speculum examination can be performed
- b. The injection of blue dye is performed after the abdomen is explored by palpation (laparotomy) or visually (laparoscopy or robotic).

- c. Clamps should not be placed on the uterus that might interfere in any way with distribution of the dye. The uterus should be manipulated by hand until blue dye is seen in the retro peritoneum.
- d. With a speculum in the vagina, inject 1 ml of isosulfan blue into four locations in the cervix.
 Use the same injection sites as with the radionuclide. A total of 4 ml of dye should be used. Allow approximately 5 minutes for the blue dye to reach the sentinel nodes.
- e. A tenaculum may be used to manipulate the cervix while injecting blue dye.
- f. Avoid spillage of blue dye into the vagina by using a narrow gauge needle (21- 25 gauge) under low pressure. A needle extender, spinal needle, or control grip syringe may be used if needed.
- g. Methylene blue, isosulfan blue, patent blue, or other blue dye compounds, depending on local availability, may be used for this procedure.

Identification of sentinel nodes

- a. Cover the hand-held gamma counter with a sterile sleeve. While waiting for distribution of blue dye, the hand held gamma counter can be used to identify "hot" nodes. The gamma probe should be fitted with a collimator if available.
- b. Incise the peritoneum lateral to the infundibular pelvic ligament and bluntly explore the retroperitoneum with care so that the afferent lymphatic channels are not transected. The afferent lymphatic channel is commonly seen adjacent to the uterine artery near the site where it passes over the ureter.
- c. All blue nodes are to be considered sentinel. If a blue channel leads directly to a lymph node but the lymph node itself is not blue, it should still be considered sentinel.
- d. Special attention to the detection of parametrial SLNs should be made. Parametrial SLNs are found medial to the superior vesical artery.
- e. Grossly involved lymph nodes that are not hot or blue should be considered SLNs and labeled "not hot, not blue SLN".
- f. The probe counts for a lymph node in-situ must be at least twice the background count in the pelvis to be considered a sentinel node.
- g. The background counts in the pelvis are determined by holding the gamma counter over the sacrum pointed away from the cervix.

- h. Following removal of the sentinel node, it should be separated from extraneous material or other non-sentinel nodes and moved off the surgical field. The gamma counter is used to determine if the node is "hot". The probe count of the lymph node should be 10 times higher than the background count of the room to be considered sentinel.
- If two sentinel nodes are adjacent to each other they should be separated and labeled as separate specimens.
- j. Following completion of the lymphadenectomy as described in section 4.1 the operative field is inspected with the gamma probe to see if there are any remaining "hot" nodes.
- k. The half-life of the radionucleotide is much longer than the blue dye and therefore is more likely to be transported to second echelon lymph nodes. For this reason there may be more "hot" nodes than "blue" nodes. The sentinel node usually retains higher counts than second echelon nodes; however this may be difficult to distinguish intraoperatively. Therefore, all "hot" nodes should be submitted as sentinel (label as described in Appendix 3).
- I. A laparoscopic gamma probe must be used to identify hot sentinel nodes in-vivo in patients undergoing laparoscopic or robotic procedures.

Injection of Indocyanine Green (IC-Green™)

- a. The patient must be positioned, prepped and draped so that a speculum examination can be performed
- b. The injection of IC-Green™ is performed after the abdomen is explored by palpation (laparotomy) or visually (laparoscopy or robotics).
- c. Clamps should not be placed on the uterus that might interfere in any way with distribution of the dye. The uterus should be manipulated by hand until IC-Green™ is seen in the retro peritoneum.
- d. With a speculum in the vagina, the concentration used should be 1.25 mg/mL. For each patient, a 25 mg vial with IC-Green™ powder is diluted in 20 cc of aqueous sterile water. Four cc of this IC-Green™ solution is injected into the cervix alone divided into the 3- and 9-o'clock positions, with 1 cc deep into the stroma and 1 cc submucosally on the right and the left of the cervix, usually prior to initiating laparoscopic or robotic entry. Allow approximately 5 minutes for the IC-Green™ to reach the sentinel nodes. Please note that when using IC-Green™, blue dye or radionuclide is not necessary.

- e. A tenaculum may be used to manipulate the cervix while injecting IC-Green™.
- f. Avoid spillage of IC-Green™ into the vagina by using a narrow gauge needle (21- 25 gauge) under low pressure. A needle extender, spinal needle, or control grip syringe may be used if needed.

• Identification of sentinel nodes

- a. Incise the peritoneum lateral to the infundibular pelvic ligament and bluntly explore the retroperitoneum with care so that the afferent lymphatic channels are not transected. The afferent lymphatic channel is commonly seen adjacent to the uterine artery near the site where it passes over the ureter.
- b. All green nodes are to be considered sentinel. If a green channel leads directly to a Lymph node but the lymph node itself is not green, it should still be considered sentinel.
- c. Special attention to the detection of parametrial SLNs should be made. Parametrial SLNs are found medial to the superior vesical artery.
- d. Grossly involved lymph nodes that are not green should be considered SLNs and labeled "not hot, not green SLN".
- e. Following removal of the sentinel node, it should be separated from extraneous material or other non-sentinel nodes and moved off the surgical field.
- f. If two sentinel nodes are adjacent to each other they should be separated and labeled as separate specimen

Labeling Specimens

- a. Careful description of sentinel nodes in the operating room is vital part of this study. To facilitate this process, standardized labels will be printed for use in the operating room. These labels provide information on the location, type (blue/green, hot, or both), and amount of radioactivity. Pathologists should be requested to enter all these data into the trial pathology report. The amount of radioactivity should be entered in terms of counts per second. This will allow determination of the most radioactive nodes in an individual and will not be used for comparison between patients.
- b. A sentinel node that is blue/green but not hot should be labeled "blue or green sentinel node".

- c. A sentinel node that is hot but not blue/green should be labeled "hot sentinel node".
- d. A sentinel node that is both blue/green and hot should be labeled "blue or green/hot sentinel node".
- e. Sentinel nodes should be labeled by location using the following categories and definitions:
 - Para-aortic: Sentinel nodes between the origin of the inferior mesenteric artery
 and bifurcation of the aorta. In addition, these nodes should be labeled right, left,
 or inter-aortic (between the inferior vena cava and aorta). Retroaortic or retrocaval
 locations are also acceptable for labeling the nodes resected from behind these
 vessels.
 - Common iliac: Sentinel nodes between the bifurcation of the aorta and bifurcation
 of the common iliac artery. Sentinel nodes should be labeled "right" or "left".
 Retroiliac nodes can be specified if appropriate.
 - External iliac: Any sentinel node in contact with the external iliac vein or artery.
 Sentinel nodes should be labeled "right" or "left".
 - Obturator: Any sentinel node that is apparent after the obturator space is opened and is in close proximity to the obturator nerve. Sentinel nodes should be labeled "right" or "left".
 - Parametrial: Sentinel nodes that are in the lateral parametrium are usually adjacent to the uterine artery and are clearly not in the other groups described above. These sentinel nodes should also be labeled "right" or "left". Medial parametrial nodes are usually not visible and may be quite small. In addition, the gamma probe cannot separate medial parametrial nodes from the high radioactivity originating from the cervix. Parametrial sentinel nodes have been described infrequently in other series.
 - Presacral: Sentinel nodes that are in the posterior lymphatic trunks of the cervix traverse the pararectal space to presacral nodes. These have been described infrequently in previous studies. When present, they are usually medial to the common iliacs and directly over the sacrum.

